**Idiopathic Pulmonary Fibrosis** 

To test the equality of distributions of times to first IPF worsening in the two treatment arms, the Log-Rank test will be applied with the following null-hypothesis:

 $H_0$ :  $S_{1t} = S_{2t}$  (the survival functions are identical in the two treatment arms)

The alternative hypothesis is:

 $H_1: S_{1t} \neq S_{2t}$  (the survival functions are not identical)

This hypothesis will be tested at a two-sided 0.05 level.

The analysis will be performed on the Full Analysis Set (FAS).

### 13.4. Sensitivity and Supportive Analyses for the Secondary Efficacy Variable(s)

For those subset of subjects who were compliant with the protocol and completed the DBT and OLE Phases, the analysis of 6MWT will be repeated. If this subset of subjects does not differ from FAS then the analysis will not be repeated.

#### 14. SAFETY AND TOLERABILITY ANALYSIS

All safety analyses will be performed for subjects in the safety analysis set.

The analysis of safety assessments in this study will include summaries of the following categories of safety and tolerability data collected for each subject:

- Treatment Emergent Adverse Events:
  - Clinical laboratory Treatment Emergent Adverse Events
  - Discontinuation due to TEAEs
  - Treatment Emergent Serious Adverse Events
- Pregnancies (if any reported)
- Clinical Laboratory Investigations
- Hemodynamics (vital signs)
- ECG Investigations
- Physical examinations
- Body weight

The analysis of safety assessments will be done for the DBT Phase and OLE Phase separately.

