4.2. Prior Clinical Experience

4.2.1. Clinical Study Overview

To date, a total of 11 clinical trials have been conducted with MN-001 and over 600 subjects have been dosed. Single and multiple doses of MN-001 ranging from 80 mg to 2000 mg for up to 12 weeks in 6 Phase 1 trials, 4 Phase 2 trials and 1 Phase 3 trial have been evaluated in healthy subjects and patients with asthma and interstitial cystitis. A summary of completed trials is provided in Table 5.

Phase 1 Studies

In the single dose studies of 80 mg to 600 mg, there appeared to be few adverse events. The most common treatment emergent adverse events (TEAEs) were mild diarrhea, sensation of

borborygmus, and heavy headedness. No clinically significant changes in vital signs, ECGs, and safety labs were observed.

In two multi-dose studies (Study KCA-757 and Study 478-02), MN-001 250 mg to 1000 mg bid was administered for approximately 7 days in healthy volunteers and subjects with mild bronchial hypersensitivity. No serious adverse events were reported and no subjects discontinued the study due to an adverse event. The most common AEs experienced in study 478-02 were upper abdominal pain (reported by 1 subject each in the 500 mg and 750 mg groups), loose stools (reported by 1 subject each in the 500 mg and 1000 mg groups), and nausea (reported by 1 subject each in the 750 mg and 1000 mg groups). The Investigator considered the following treatment-emergent AEs to be possibly or probably related to study drug (treatment group in parentheses): abdominal pain (placebo), upper abdominal pain (500 mg and 750 mg), dyspepsia (1000 mg), fatigue (placebo), loose stools (500 mg and 1000 mg), nausea (750 mg and 1000 mg), somnolence (750 mg), urine odor abnormal (500 mg).

In study 478-02, vital signs were within normal limits. All mean ECG measurements remained within normal limits. At Hour 359.67 mean QTc for the 750 mg group increased 27.66 ms from baseline for a mean QTc of 395.83 ms and mean heart rate increased 14.50 bpm from baseline for a mean heart rate of 70.67 bpm. No other marked mean changes from baseline were noted. The Investigator considered none of the ECG abnormalities in this study to be adverse events.

All treatment groups, including the placebo group, exhibited notable mean increases in CPK (ranging from approximately 22 to 135 U/L) at Hour 360. No other marked mean changes from baseline were noted for the remaining serum chemistry parameters.

High Doses of MN-001 (1500 mg/day)

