### 5.2.2. Secondary Outcome Variable(s)

- Semiannual/Annual rate of decline in disease activity based on the 6-minute walk test (6MWT):
  - Change in 6MWT distance
- Change from baseline in disease activity based on Modified Medical Research Council Dyspnea Score (MMRC):
  - MMRC score is a single score, assigned on a scale of 5 levels (0 [best] to 4 [worst])
- Change from baseline in quality of life (QOL) measured by A Tool to Assess Quality of Life in Idiopathic Pulmonary Fibrosis (ATAQ-IPF):
  - The ATAQ-IPF questionnaire has 13 domains (Cough, Dyspnea, Forethought, Sleep, Mortality, Exhaustion, Emotional Well-being, Social Participation, Finances, Independence, Sexual Health, Relationships, Therapy). The domain scores and Total score from these domain scores are calculated by summation. Higher scores correspond to greater impairment.
  - For statistical analysis, the *Total score* will be used as outcome variable which ranges from 74 to 370.
- Frequency of worsening IPF
  - Worsening of IPF is defined as:
    - o acute IPF exacerbation
    - o hospitalization due to respiratory symptoms
    - o IPF related fatal events
    - o lung transplantation
- Time to first worsening of IPF

Safety will be assessed by the proportion of subjects with the following events:

- Clinical and laboratory treatment emergent adverse events (TEAEs)
- Discontinuations due to TEAEs
- Treatment emergent serious adverse events (TESAEs)

Safety (relationship and severity of AEs) and tolerability will further be assessed by statistical and clinical review of AEs, laboratory values, ECGs, physical examinations, vital signs and weight.

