#### 6. STUDY METHODS

### 6.1. Overall Study Design and Plan

This is a randomized, placebo-controlled, double-blind 6-month study followed by a 6-month open-label extension phase to evaluate the efficacy, safety, and tolerability of MN-001 in moderate to severe IPF patients. MN-001 750 mg or matching Placebo will be orally administered twice daily over a 26-week period in subjects with a confirmed diagnosis of moderate to severe IPF per the ATS 2011 Guidelines (Raghu et al, 2011).

Approximately 15 subjects are planned to be enrolled. This study will consist of two treatment arms, MN-001 and matching Placebo. Randomization will occur in a 2:1 ratio (MN-001:Placebo). Eligible subjects will consist of males and females ranging in age from 21 to 80 years old, inclusive. The study will consist of a Screening Phase (up to 3 months prior to Day 1) followed by a 26-week double-blind Treatment Phase, a 26 week Open-Label Extension (OLE) phase and a Follow-up Visit (within 4 weeks after the last dose).

Overall study design and plan is described in detail in Final Protocol Amendment 1, Section 6. Overall Study Design and plan: Description.

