#### 10.1. Definition of Treatment Arms

Treatment arms will be denoted as follows in the TLFs:

- "MN-001" 750 mg of MN-001 administered orally twice daily
- "Placebo" Matching Placebo administered orally twice daily
- "Former Placebo" Matching Placebo administered orally twice daily during the Double-Blind Treatment Phase and 750 mg of MN-001 administered orally twice daily during the OLE Phase

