#### 14.1. Adverse Events

Adverse events (AEs) will be coded using the Medical Dictionary for Regulatory Activities (MedDRA) central coding dictionary, version 21.0.

Summary tables for AEs will include treatment-emergent adverse events (TEAEs, defined as AEs occurred during or after the first administration of a study drug). AEs occurred before the first administration of a study drug will be listed separately. Aes occurring 7 days after the last dose of study medication will be listed separately.

Unless otherwise stated, AE analyses will be subject-based, each subject will be counted once in frequency tables at the subject, SOC and preferred term levels, and the denominator for percentages will be the number of subjects in the SAS, in the respective treatment arm (i.e. "as treated" assignment of treatment arms).

AEs will be assigned to study phases (DBT or OLE) based on their start date.

If the start date of an AE is incomplete:

a/ If only day is missing, and if in the same month the treatment was started then the start date of AE will be imputed with the day of first treatment. If treatment started earlier and not in that month then the first day of the month will be used for imputation.

b/ If month and day are missing, and the treatment start date was in the same year then the start date of AE will be imputed with the month and day of the first treatment administration. If the treatment start date was in the previous year, then 01 JAN will be used for imputation.

c/ If the entire AE start date is missing then the date will not be imputed, but the AE will be considered treatment-emergent.

If the end date of an AE is missing, the AE will be considered as "ongoing".

If a subject xperiences a TEAE with a missing causality assessment, then relationship will be categorized as "Related". AEs with a missing causality assessment during the screening period relationship will be categorized as "Unrelated".

If a subject experiences a TEAE with a missing severity assessment, then severity for this TEAE will be categorized as "Severe".

In addition to keeping the 5-level categorization of causality of AEs, they will also be dichotomized into two categories: related/not related. "Related" category comprises events which were classified by the investigator as possibly, probably or related to treatment, whereas "Not Related" category comprises the other two levels of the investigator's assessment ("Unlikely to be related" and "Unrelated").

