#### 14.1.1. All Adverse Events

An overview of number of subjects (%) with treatment-emergent AEs will be presented for the main AE categories (All AEs, AEs leading to discontinuation, SAEs, SAEs leading to discontinuation, AEs with at least Grade 3 severity (Severe AEs, Life-threatening AEs, Deaths), AEs and SAEs with relationship to IMP as possibly related, probably related, or related) by treatment arm and phase.

The number (%) of subjects with treatment-emergent AEs will be presented by phase, treatment arm, System Organ Class and Preferred Term (MedDRA), AE severity, and relationship to study drug (for both AEs and SAEs). Each subject will be counted only once within each preferred term per study phase. If a subject experiences more than one AE within a preferred term for the same recording phase, only the AE with the strongest relationship or highest severity, as appropriate, will be included in the summaries by relationship and severity.

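### With safety tabulated by phase and no all-MN-001 summary, the planned tables do not give the cumulative proportion of exposed subjects with an event that can recur

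*SAP*

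**What the plan says.** The general rule for safety is in SAP section 14: "The analysis of safety assessments will be done for the DBT Phase and OLE Phase separately". Section 14.1 adds the allocation rule, "AEs will be assigned to study phases (DBT or OLE) based on their start date", and the percentage base, "the denominator for percentages will be the number of subjects in the SAS, in the respective treatment arm". Section 14.1.1 presents both the overview of adverse event categories and the system organ class and preferred term tables by arm and phase. Its counting rule is "Each subject will be counted only once within each preferred term per study phase".

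SAP section 10.1 defines three reporting groups: MN-001, Placebo and Former Placebo. The last is described as "Matching Placebo administered orally twice daily during the Double-Blind Treatment Phase and 750 mg of MN-001 administered orally twice daily during the OLE Phase". No group covers everyone who received MN-001.

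On the endpoint, SAP section 5.2.2 says "Safety will be assessed by the proportion of subjects with the following events", and then names TEAEs, discontinuations due to TEAEs, and serious TEAEs. Protocol section 11 has the same list. Protocol section 13.1.4 asks for incidence by treatment group and is silent on phase.

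**The concern.** The safety endpoint is a proportion of subjects. For a subject randomised to MN-001, treatment runs across both phases, about 52 weeks in all (Protocol synopsis, duration of treatment). The natural question is how many of those who took the drug had the event at any time on it. The planned tables answer a different question twice, once per phase, and the same people sit in both MN-001 columns.

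This matters because longer exposure is much of what the study adds. Protocol section 4.2.1 describes earlier experience as "Single and multiple doses of MN-001 ranging from 80 mg to 2000 mg for up to 12 weeks". The study is a pilot intended to inform later designs, and a later design would want the cumulative proportion of exposed subjects with, say, diarrhoea.

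Overlap between the columns is also likely in practice. Protocol section 12.2.1 has a change in severity recorded as a new adverse event with its own date. One continuing complaint that changes grade after Month 6 would therefore put the same subject in both phases.

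**Working it through.** There is no plan figure to reproduce: the sample size is given without a derivation, and the point does not depend on one. The check is a counting argument.

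**Inputs**
- Planned size: "Approximately 15 subjects are planned to be enrolled" (SAP section 6.1).
- Allocation 2:1 (SAP section 6.1), so n = 15 × 2/3 = 10 on MN-001 and 15 − 10 = 5 on placebo.
- Counting once per subject within each phase (SAP section 14.1.1).
- The event counts below are assumptions chosen to illustrate; the documents give none.

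**Does another rule in the plan settle it?** Section 14.1 says each subject is counted once in frequency tables, but only where nothing else is stated. Section 14.1.1 does state something else: tables by phase, with counting per phase. So the general rule does not produce a cumulative count.

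**Bounds for the MN-001 arm.** Let a be the number affected in the double-blind phase and b the number affected in the open-label phase. If the smaller group lies wholly inside the larger, the number ever affected is max(a,b). If the groups overlap as little as possible, it is min(a+b,n). The tables do not say where in this range the truth lies.

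**All exposed subjects.** Former Placebo subjects receive MN-001 only in the open-label phase, so their count f is exact and is added to both ends of the range, over 10 + 5 = 15. If one or two placebo subjects never start open-label drug, the denominator is 14 or 13.

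| a | b | f | MN-001 arm, of 10 | All exposed, of 15 |
|---|---|---|---|---|
| 4 | 3 | 2 | 4 to 7 (40% to 70%) | 6 to 9 (40% to 60%) |
| 5 | 5 | 2 | 5 to 10 (50% to 100%) | 7 to 12 (47% to 80%) |
| 2 | 2 | 1 | 2 to 4 (20% to 40%) | 3 to 5 (20% to 33%) |
| 3 | 0 | 1 | 3 (30%) | 4 (27%) |

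**Largest gap.** The width of the range is min(a+b,n) − max(a,b). For n = 10 it is greatest at a = b = 5, where it is 10 − 5 = 5 subjects. That is 5/10 = 50 percentage points in the MN-001 arm and 5/15 = 33 points over all exposed.

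**Where there is no gap.** If either phase count is zero, the range closes, as in the last row. Death and discontinuation due to an adverse event happen at most once per subject, so a + b is exact for them. SAP section 11.1 also tabulates withdrawals by reason and arm, with no stated split by phase.

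**The case against.** The strongest case against is that nothing is lost. SAP section 10 has all clinical data listed. Sections 14.1.2 to 14.1.4 give separate listings for withdrawals due to adverse events, serious events and deaths. Section 12.4 lists dosing days. With about 15 subjects, anyone can count by hand. Section 3.2 also allows further exploratory analyses. Separating blinded, controlled data from open-label data is good practice, and neither document requires a pooled exposure table or rates per subject-year.

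Most of that is true, and it limits the point to the planned summaries. It does not remove it. A total assembled by hand after the results are known is not a prespecified summary of an endpoint that the SAP defines as a proportion of subjects. The SAP also accepts the principle elsewhere: section 13.3 estimates the 6-minute walk slope for the MN-001 arm across both phases together.

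Two stronger readings are tempting, and the documents do not support either.
- A reader might infer that the plan says nothing about MN-001 after six months. It does: the open-label MN-001 column reports subjects with events in Months 6 to 12. Only the cumulative figure is missing.
- A reader might infer that a combined column would bring in more subjects or more exposure, and so a better chance of seeing an uncommon event. It would not. Former Placebo open-label events are already tabulated, so a case in any exposed subject appears in some planned table. If every column shows zero, the columns already add to 0/15.

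**Conclusion.** The point holds in a limited form. For events that can recur (any TEAE, serious TEAEs, Grade 3 or higher, related events, each system organ class and preferred term), the planned tables fix the cumulative proportion in the MN-001 arm only to a range. On a 10:5 split that range can be as wide as 50 percentage points in the MN-001 arm and 33 points over all exposed subjects. Its actual width depends on the observed counts, and it is nil when one phase has no events.

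The result rests on the 2:1 allocation of about 15 subjects being achieved, and on the section 14.1.1 counting rule being applied as written. It is a reporting gap: the double-blind comparison with placebo is unaffected and no data are missing. It is worth correcting because the correction is cheap.

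**What to change.** Keep the phase tables. Define an All MN-001 group in SAP section 10.1 and add one adverse event summary for it in section 14.1.1:

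- Start at each subject's first MN-001 dose: Day 1 for the MN-001 arm, the first open-label dose for Former Placebo. Anchor on the dose and not on the phase boundary, because SAP section 10.2 starts the open-label phase on the day after Visit 8 while Protocol section 8.8.1.2 treats the Month 6 visit as its first day.
- Use the SAP's TEAE definition and state where it ends. Section 15 says that the protocol's definition was changed, but section 14.1 does not give a clear end point.
- Count each subject once per category, system organ class and preferred term over the whole period.
- Give n/N and the number of subjects with events per subject-year of exposure.
- Show the MN-001 arm (up to 52 weeks) and Former Placebo (up to 26 weeks) separately as well as pooled, because their exposure lengths differ.

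The cost is a new group definition, an exposure-time derivation and one table that crosses phases. All the inputs are already collected. The downside is that the summary is uncontrolled and, when pooled, mixes exposure lengths, so it must be labelled accordingly. If treatment codes have already been opened, report it as unplanned, as SAP section 3.2 requires.

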#### 14.1. Adverse Events

Adverse events (AEs) will be coded using the Medical Dictionary for Regulatory Activities (MedDRA) central coding dictionary, version 21.0.

Summary tables for AEs will include treatment-emergent adverse events (TEAEs, defined as AEs occurred during or after the first administration of a study drug). AEs occurred before the first administration of a study drug will be listed separately. Aes occurring 7 days after the last dose of study medication will be listed separately.

Unless otherwise stated, AE analyses will be subject-based, each subject will be counted once in frequency tables at the subject, SOC and preferred term levels, and the denominator for percentages will be the number of subjects in the SAS, in the respective treatment arm (i.e. "as treated" assignment of treatment arms).

AEs will be assigned to study phases (DBT or OLE) based on their start date.

If the start date of an AE is incomplete:

a/ If only day is missing, and if in the same month the treatment was started then the start date of AE will be imputed with the day of first treatment. If treatment started earlier and not in that month then the first day of the month will be used for imputation.

b/ If month and day are missing, and the treatment start date was in the same year then the start date of AE will be imputed with the month and day of the first treatment administration. If the treatment start date was in the previous year, then 01 JAN will be used for imputation.

c/ If the entire AE start date is missing then the date will not be imputed, but the AE will be considered treatment-emergent.

If the end date of an AE is missing, the AE will be considered as "ongoing".

If a subject xperiences a TEAE with a missing causality assessment, then relationship will be categorized as "Related". AEs with a missing causality assessment during the screening period relationship will be categorized as "Unrelated".

If a subject experiences a TEAE with a missing severity assessment, then severity for this TEAE will be categorized as "Severe".

In addition to keeping the 5-level categorization of causality of AEs, they will also be dichotomized into two categories: related/not related. "Related" category comprises events which were classified by the investigator as possibly, probably or related to treatment, whereas "Not Related" category comprises the other two levels of the investigator's assessment ("Unlikely to be related" and "Unrelated").

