#### 9. ANALYSIS POPULATIONS

The following analysis populations are planned for the studies:

- **Full Analysis Set (FAS)** will include all enrolled subjects who receive at least one dose of study medication and have at least one post efficacy assessment.
- **Safety Analysis Set (SAS)** will include all subjects who received at least one dose of study drug and had at least one post dose safety assessment.

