### **10.2.** Definition of Study Phases

Double Blind Treatment Phase (DBT Phase)

The DBT Phase starts with Visit 3 which is the Day 1 of the DBT phase.

The DBT Phase ends with end of the day of Visit 8 (Month 6) and assessments taken on this visit will be considered as belonging to the DBT phase.

Open Label Extension Phase (OLE Phase)

The OLE Phase starts on the following day of Visit 8 and ends with Visit 14(Month 13).

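### SAP 14.1 gives adverse-event percentages no phase-specific denominator, so any MN-001 subject who withdraws before Month 6 lowers the open-label MN-001 percentages

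*SAP*

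**What the plan says.** The denominator rule is in SAP section 14.1. For adverse-event tables, "the denominator for percentages will be the number of subjects in the SAS, in the respective treatment arm", with arms assigned as treated. The rule allows for exceptions stated elsewhere, but none is given for the open-label extension (OLE).

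SAP section 9 defines the Safety Analysis Set once for the whole study: it "will include all subjects who received at least one dose of study drug and had at least one post dose safety assessment". Sections 9 and 9.1 define no open-label safety set.

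Reporting is nevertheless by phase. Section 14 says: "The analysis of safety assessments will be done for the DBT Phase and OLE Phase separately". Section 14.1 adds: "AEs will be assigned to study phases (DBT or OLE) based on their start date". Section 14.1.1 says: "The number (%) of subjects with treatment-emergent AEs will be presented by phase, treatment arm", among other factors, and "Each subject will be counted only once within each preferred term per study phase". Section 10.2 fixes the boundary between the double-blind treatment (DBT) phase and the OLE: "The OLE Phase starts on the following day of Visit 8 and ends with Visit 14(Month 13").

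Section 10.1 uses the single label MN-001 for that arm throughout the study. It defines the other open-label arm, Former Placebo, as "Matching Placebo administered orally twice daily during the Double-Blind Treatment Phase and 750 mg of MN-001 administered orally twice daily during the OLE Phase".

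**The concern.** The numerator of an open-label percentage is specific to the phase, because events are placed by start date. The written denominator is not. A subject randomised to MN-001 who leaves the study before Visit 8 has no open-label follow-up and cannot add to the numerator, but still belongs to the Safety Analysis Set and to the MN-001 arm.

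The safety endpoints in SAP section 5.2.2 are proportions of subjects with treatment-emergent events, serious events and discontinuations due to events. For the MN-001 arm, the open-label table is where months 7 to 12 of exposure are described, and the sponsor intends to use the results to design later studies. Under the written rule, the more MN-001 subjects stop early, the lower the open-label percentages become.

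The two open-label columns would also rest on different bases: everyone ever dosed for MN-001, and only those who crossed over for Former Placebo. A reader comparing them side by side would not be told this.

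**Working it through.** The documents state no adverse-event rate and no dropout rate, so there is no figure of the plan's own to reproduce. The check is direct arithmetic on the written rule.

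**Inputs**
- Planned size: about 15 subjects, randomised 2:1 (SAP sections 6.1 and 8). Arm sizes: 15 × 2/3 = 10 on MN-001 and 15 × 1/3 = 5 on placebo. This assumes that all are dosed and enter the Safety Analysis Set.
- Withdrawals before Month 6 in the MN-001 arm: not stated. Assumed range w = 0 to 4.
- Number of MN-001 subjects with an open-label event: x = 3, for illustration.

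**Formulas**
- Percentage under the SAP rule: x / n, with n = 10.
- Percentage among those who entered the OLE: x / (n − w).
- Ratio of the first to the second: (n − w) / n = 1 − d, where d = w / n. The ratio does not depend on x.

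**Open-label MN-001 column, n = 10, x = 3**

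| Withdrew before Month 6 | Entered OLE | SAP rule | Among entrants | Factor |
|---|---|---|---|---|
| 0 | 10 | 3/10 = 30.0% | 3/10 = 30.0% | 1.0 |
| 1 | 9 | 3/10 = 30.0% | 3/9 = 33.3% | 0.9 |
| 2 | 8 | 3/10 = 30.0% | 3/8 = 37.5% | 0.8 |
| 3 | 7 | 3/10 = 30.0% | 3/7 = 42.9% | 0.7 |
| 4 | 6 | 3/10 = 30.0% | 3/6 = 50.0% | 0.6 |

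**Former Placebo column.** A placebo subject who left before Month 6 never took MN-001 in the OLE and so does not meet the section 10.1 definition. On that reading the denominator is already the number who crossed over, and the factor is 1.0. Only if a programmer used all 5 randomised placebo subjects instead would the factor fall, to 4/5 = 0.8 with one withdrawal or 3/5 = 0.6 with two.

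**Effect on the two columns together.** Suppose 8 of 10 MN-001 and 4 of 5 placebo subjects enter the OLE, and half of each group has an event. Among entrants, both columns read 50% (4/8 and 2/4). Under the written rule, MN-001 reads 4/10 = 40% and Former Placebo 2/4 = 50%.

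**Double-blind columns.** Every subject in the Safety Analysis Set took at least one dose; under the planned flow that first dose falls in the DBT phase, so each belongs in that phase's denominator. Nothing changes there.

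**The case against.** The best defence is that the rule is incomplete rather than wrong. It refers to as-treated arms and leaves room for exceptions, and section 14 calls for separate analysis by phase, so a sensible programmer might take the open-label N without being told. That may happen, but the tables would then rest on a reading the SAP does not state, and two programmers could produce different percentages from the same text.

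Several stronger readings are tempting, and the documents do not support them.

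- *That both phases, or all arms, are affected.* The denominator is set within the arm. Double-blind percentages are sound, and Former Placebo as defined excludes subjects who did not cross over. What remains is the MN-001 column in the open-label phase.
- *That open-label percentages will certainly be too low.* The effect is zero if nobody on MN-001 leaves before Month 6. Withdrawals are foreseen (protocol section 7.3, SAP section 11.1), but no rate is given. Protocol Table 4 shows 131 of 147 completing a 4-week asthma trial (16/147 = 11% lost) and 251 of 305 an 8-week interstitial cystitis trial (54/305 = 18% lost). Those are other diseases with all arms pooled, so they cannot supply a rate for 26 weeks in this population.
- *That early toxicity is hidden.* Subjects who stop in the double-blind phase still appear in that phase's discontinuation rows, in the listing of events leading to withdrawal, and in disposition by arm and reason. Counts are printed beside percentages, so a careful reader could probably rebuild the denominator.
- *That the percentage among entrants is the true rate.* It describes a selected group who stayed. It is the better descriptive base for an open-label table, but no more than that.
- *That a planned comparison is biased.* The SAP specifies no safety test of MN-001 against Former Placebo. Such a contrast would in any case set later exposure against first exposure.
- *That laboratory percentages share the fault.* The rule covers adverse-event analyses. SAP section 14.3 states no denominator for laboratory incidence, so no error is shown there.

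**Conclusion.** The point holds in a limited form. SAP 14.1 states a denominator that does not fit the open-label adverse-event tables. If any MN-001 subject withdraws before Month 6, the open-label MN-001 percentages for adverse events, serious adverse events and discontinuations are understated by the factor 1 − d relative to subjects who entered that phase. The size is an assumed range because pre-Month-6 withdrawal is not quantified for this trial: no understatement without withdrawals, a tenth of the value for each withdrawal in a 10-subject arm, and four tenths at the top of the range shown.

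The conclusion rests on an arm of 10 and on reading 14.1 as written. The primary lung-function analysis and the double-blind safety comparison are not touched. It should be corrected because it is a written rule that misdescribes one column and leaves the two open-label columns on unequal bases, and because correcting it is easy.

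**What to change.** In SAP section 14.1, keep the present denominator (Safety Analysis Set subjects in the as-treated arm) for the DBT phase. Add one sentence: for the OLE phase, adverse-event percentages use the Safety Analysis Set subjects who took at least one open-label dose, by arm (MN-001 and Former Placebo). Show that N in the column headers of every open-label adverse-event table, including those for serious events and discontinuations.

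The cost is one sentence and one programming flag. No new data are needed. Open-label MN-001 percentages may become slightly less favourable.
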